1

2

3 **STUDY PROTOCOL**

4 **Cervical Pessary for Prevention of Spontaneous Preterm Birth in Singleton Pregnancies** 5 **without prior preterm birth and with short cervix: a randomized controlled trial**

6

7

8

9

10

11

12

13

14

15 **Abbreviation:** TVU, transvaginal ultrasound; CL, cervical length; PTB, preterm birth; SPTB,
16 spontaneous preterm birth; OR, odds ratio; CI, confidence interval; GA, gestational age; RCT,
17 randomized controlled trials; GCP, Good Clinical Practice; SD, standard deviation

18

19

20

21

22

23

24

25

26

27

28

29

30

31

32

33 **SUMMARY**

Title	Cervical Pessary for Prevention of Spontaneous Preterm Birth in Singleton Pregnancies without prior preterm birth and with short cervix: a randomized controlled trial.
Study location	University of Naples Federico II
Objective	To test the hypothesis that in asymptomatic singleton pregnancies without prior SPTB but with short TVU CL the insertion of a cervical pessary would reduce the rate of SPTB <34 weeks
Study design	Single center prospective randomized trial
Study population	Asymptomatic singleton gestations without prior SPTB and with TVU CL ≤ 25 mm
Exclusion criteria	
 - Multiple gestations - Prior SPTB - Rupture membranes, cerclage or pessary, or vaginal bleeding at the time of randomization - Major fetal abnormalities - Chromosomal abnormalities

GA at randomization	18 0/7 – 23 6/7
Duration of study period	2 years (1 year enrollment + 1 year data analysis)
Estimated study period for enrollment	October 2016 – October 2017
Estimated sample size	300 singleton pregnancies
Primary outcome	SPTB <34 weeks

34

35

36

37

38

39

40

41

42

43

44

45

46 INTRODUCTION

47 Preterm birth (PTB) is a major cause of perinatal morbidity and mortality. Worldwide, about 15
48 million babies are born too soon every year, causing 1.1 million deaths, as well as short- and
49 long-term disability in countless survivors.

50 Different strategies have been studied for prevention of spontaneous PTB (SPTB) in randomized
51 controlled trials (RCTs), including progesterone, cerclage, cervical pessary, as well as lifestyle
52 modification, such as smoking cessation, diet, aerobic exercise, and nutritional supplements.

53 Most successful effort to reduce the incidence of SPTB have focused on women with risk
54 factors, such as prior SPTB. However, most SPTB occur in women who have no such history.

55 The evidence supports the use of vaginal progesterone in singleton gestations without prior
56 SPTB but with short transvaginal ultrasound (TVU) cervical length (CL). Based on this
57 evidence, universal TVU CL has been proposed for all singleton gestations without prior SPTB
58 as a screening method for SPTB.

59 The cervical pessary is a silicone device that has been used to prevent SPTB. The leading
60 hypotheses for its mechanisms are two: that the pessary helps to keep the cervix closed, and that
61 the pessary changes the inclination of the cervical canal so that the pregnancy weight is not
62 directly above the internal os.

63

64

65

66

67 **STUDY OBJECTIVES**

68 Thus, we aim to test the hypothesis that in asymptomatic singleton pregnancies without prior
69 SPTB but with short TVU CL the insertion of a cervical pessary would reduce the rate of SPTB
70 <34 weeks.

71

72

73

74

75

76

77

78

79

80

81

82

83

84

85 METHODS**86 STUDY DESIGN**

87 The trial will be conducted in compliance with the protocol, Good Clinical Practice (GCP), and
88 applicable regulatory requirements.

89 This will be a prospective, single center randomized trial of asymptomatic singleton pregnancies
90 without prior SPTB but with short TVU CL who will be randomized to either pessary (i.e.
91 intervention group) or no pessary (i.e. control group) at Division of High Risk Pregnancy,
92 Departement of Obstetrics and Gynecology, University of Naples Federico II (Napoli, Italy)

93 INCLUSION AND EXCLUSION CRITERIA

94 Eligible women will be those referred to our Insitution due to a diagnosis of short cervix during
95 the routine anatomy scan. In our Division, the measurement of the cervix by using TVU will be
96 repeat and those found to have TVU CL ≤ 25 mm will be approached by the research staff and
97 consented. An information leaflet concerning the study will be given to the women.

98 *Inclusion criteria are:*

- 99 - Singleton gestations
- 100 - No prior SPTB
- 101 - 18-50 years of age
- 102 - TVU CL ≤ 25 mm

103 *Exclusion criteria are:*

- 104 - Multiple gestations

- 105 - History of SPTB in a prior pregnancy
- 106 - Rupture of membranes at the time of randomization
- 107 - Known major fetal structural (i.e. defined as those that are lethal or require prenatal or
- 108 postnatal surgery) or chromosomal abnormality
- 109 - Fetal death at the time of randomization
- 110 - Cerclage in situ at the time of randomization
- 111 - Pessary in situ at the time of randomization
- 112 - Vaginal bleeding at the time of randomization
- 113 - Women who are unconscious, severely ill, mentally handicapped, or under the age of 18
- 114 years.
- 115 - Placenta previa and/or accreta
- 116 - Ballooning of membranes outside the cervix into the vaginal or TVU CL = 0mm
- 117 - Painful and regular uterine contractions

118 We define prior SPTB as history of spontaneous preterm delivery between 16 0/7 and 36 6/7
119 weeks in a prior pregnancy.

120 Gestational age will be judged from the menstrual history and confirmed by measurement of
121 fetal crown-rump length at a first trimester scan or the head circumference at the anatomy scan.

122 **QUALITY CONTROL AND HANDLING OF DATA**

123 Information of the characteristics of the patients, including demographic data, measurements for
124 calculation of the BMI, and obstetrical and medical histories, will be obtained from the patients
125 at the time of the TVU CL scan and will be recorded directly on the CRFs. These will then be
126 entered into a computer database and on the subject screening log in the study site file.

127 Data on pregnancy outcomes were obtained from hospital maternity records. In case of PTB,
128 records were examined to determine whether the delivery was medically indicated (indicated
129 PTB) or spontaneous. SPTB included either spontaneous onset of labor or PPRM.

130 Quality control of screening, handling of data, and verification of adherence to protocols will be
131 performed on a regular basis by the trial coordinators.

132 The operators who will perform the TVU CL scan will have received extensive training and
133 passed a practical examination administered by an expert to demonstrate their competence in
134 cervical assessment (Fetal Medicine Foundation Certificate of Competence in Cervical
135 Assessment).

136 **MEASUREMENT OF CERVICAL LENGTH**

137 Before the TVU CL scan, women will be asked to empty the bladder, undress from the waist
138 down and to lie on an examination bed. The CL will be measured by operators with certification
139 of competence in the technique (Fetal Medicine Foundation Certificate of Competence in
140 Cervical Assessment). The length of the cervix will be measured with a transvaginal real-time
141 ultrasound probe (GE Health Care Endocavity Transducer; bandwidth 5-13 MHz; Voluson E8)
142 placed in the anterior fornix of the vaginal. Endocervical canal length will be measured as the
143 distance between the internal and external os, by using a straight line with calipers placed at the
144 notches made by the internal os and external os. The image will be enlarged while visualizing the
145 three landmarks simultaneously. This procedure will be repeated three times. After a baseline CL
146 will be measured, fundal pressure will be applied for 30 seconds as a provocative maneuver. CL
147 will be measured during and after the fundal pressure. Only the shortest CL measurement will be
148 recorded. Each examination will be performed during a minimum of five minutes.

149 INTERVENTION GROUP AND CONTROL GROUP MANAGEMENT

150 At the time of randomization, all women will undergo a speculum examination. Moreover,
151 vaginal swabs will be taken from all women in both groups for bacteriological analysis. If the
152 results will show infection, appropriate treatment will be given without delaying the insertion of
153 the pessary in the study group. The pessary will be not removed in case of evidence of bacterial
154 infection after device insertion.

155 All the cervical pessaries that will be used in the trial are certified by European Conformity
156 (CE0482, MED/CERT ISO 9003/EN 46003; [name], Witten, Germany).

157 All the pessaries will be inserted by the attendings, who had received practical training in the
158 placement of the device. Pessary insertion training consists of a didactic session and a hands-on
159 session. All staff will be required to demonstrate competence in pessary placement on a live
160 model.

161 Women in the control group will receive the same obstetrical care as those in the study group.
162 All the participants will be followed in outpatient settings every month until delivery. In the
163 pessary group, a digital exam will be done at each of these monthly visits to assure proper
164 pessary placement. At any follow-up visit, TVU CL and assessment of adverse events will be
165 recorded. For TVU CL ≤ 20 mm, women in both groups will be all recommended vaginal
166 progesterone 200mg suppositories daily until 36 6/7 weeks.

167 No bed rest or activity restriction will be recommended. Abstain from vaginal intercourse will
168 also not recommended.

169 In the study group, the Arabin pessary will be placed at the time of randomization and will be
170 removed during the 37th weeks (37 0/7 – 37 6/7) or early if clinically indicated. Reason for early
171 removal includes active vaginal bleeding, preterm labor with persistent contractions and
172 advanced dilatation despite tocolysis, severe discomfort, or subject request.

173 **RANDOMIZATION AND MASKING**

174 After written informed consented will be obtained from the eligible participants, women will be
175 randomly allocated in a 1:1 ratio to either the pessary group or control group. Women were
176 randomized by a web-based system (randomization.com) using random blocks of 2,4 and 6 to
177 receive the pessary or no pessary. Randomization will be stratified by CL (CL \leq 20mm, CL
178 $>$ 20mm – 25mm).

179 The randomization sequence will be prepared by an independent statistician (at Division of
180 Statistics, Department of Law, Economics, Management and Quantitative Methods, University of
181 Sannio, Benevento, Italy) and implemented by use of central telephone. The recruiters or the trial
182 coordinator will not have access to the randomization sequence. The allocation code will not be
183 disclosed after the patient's initials are confirmed. The study will be open label because of the
184 nature of the intervention, but the outcome assessors, data collectors, and data analysts will
185 blinded to the allocated treatment group.

186 **PRIMARY AND SECONDARY OUTCOMES**

187 The primary outcome is SPTB $<$ 34 weeks

188 The secondary outcomes are:

189 - SPTB $<$ 37, $<$ 32, and $<$ 28 weeks

- 190 - Mean gestational age at delivery in weeks
- 191 - Mean latency in days (time from randomization to delivery)
- 192 - PPROM <34 weeks
- 193 - Mode of delivery
- 194 - Maternal side effects
- 195 - Chorioamnionitis (i.e. inflammation of the chorion and amnion by histopathological
- 196 assessment after delivery)
- 197 - Birth weight
- 198 - NICU
- 199 - Neonatal death (i.e. death of a live-born baby within the first 28days of life)
- 200 - Perinatal death (either fetal or neonatal mortality)
- 201 - A composite of adverse perinatal outcome defined as at least one of the following:
 - 202 ○ NEC
 - 203 ○ IVH grade 3 or higher
 - 204 ○ RDS
 - 205 ○ BPD
 - 206 ○ ROP requiring therapy
 - 207 ○ Blood-culture proven sepsis
 - 208 ○ Neonatal death.

209 **SAMPLE SIZE**

210 The sample size calculation presented here is based on detecting an effect that produces 50%
211 reduction in the overall incidence of spontaneous preterm delivery between randomization and

212 33 6/7 weeks from an anticipated 25% in the control group (i.e. singletons with short cervix with
213 vaginal progesterone).

214 On the assumption that 60% of women with singleton gestations fulfilling the entry criteria agree
215 to participate in the study and provide follow-up data, we would be to approach about 500 such
216 women for a final sample size of 300 women. The power calculations of 300 women (150 per
217 group) were undertaken by computer simulation.

218 At our institution, we perform about 3,000 deliveries per year. However, our hospital is the one
219 of the few referral center in the Regione Campania (an area of about 55,000 deliveries per year)
220 for PTB and most of the women with short TVU CL at the routine anatomy scan are referred to
221 our institution. Therefore, we perform about 600 counselling per year on the risk of PTB in
222 singleton gestations with short cervix, of them about 500 are singleton gestations without prior
223 SPTB. Based on these data, we estimate a 2-year study period, 1 year for enrollment and 1 year
224 for data analysis.

225 **STATISTICAL ANALYSIS AND REPORTING**

226 Results will be presented according to the CONSORT statement.

227 ***Baseline data***

228 Baseline data on (LIST) for the intervention and control groups will be summarized for by the
229 median and the interquartile range. Continuous data will be summarized in terms of mean, SD,
230 minimum, maximum, and quartiles. Attribute data will be summarized on terms of frequency
231 counts and proportions

232 ***Primary analysis***

233 The primary analysis will be an intention to treat comparison of the treatment assigned at
234 randomization. The treatment effect will be tested at the two-tailed 5% level. A 95% CI will be
235 produced the OR of intervention/control group. The incidence of SPTB <34 weeks will
236 quantified by the OR with 95% CI using the logistic regression allowing for cervical length as a
237 covariate

238 *Secondary analysis*

239 The risk of SPTB <34 will be assessed with the use of Kaplan-Meier analysis, in which
240 gestational age is the time scale and spontaneous delivery the event, and elective deliveries will
241 be treated as censored. Hazard ratios will be estimated.

242 Statistical analysis will be performed using Statistical Package for Social Sciences (SPSS) (IBM
243 Inc., Armonk, NY, USA)

244 **REGULATORY ISSUES**

245 This study is approved by the local IRB at University of Naples Federico II (Comitato Etico
246 Carlo Romano) (Unina trial #213/15)

247 **FUNDING**

248 No financial support will be received for this study

249

250

251

252 **REFERENCES**

254 items for trials. *Int J Surg*, 2015; 13:288-91

255 Altman DG. *Practical statistics for medical research*. London: Chapman and Hall, 1991

256 Berghella V, Ludmir J, Simonazzi G, Owen J. Transvaginal cervical cerclage: evidence for
257 perioperative management strategies. *Am J Obstet Gynecol*, 2013; 209:181-92

258 Berghella V, Odibo AO, To MS, Rust OA, Althuisius SM. Cerclage for short cervix on
259 ultrasonography: meta-analysis of trials using individual patient-level data. *Obstet Gynecol*,
260 2005; 106:181-9

262 *Rep*, 2012; 61:1-20

263 Khalifeh A, Berghella V. Universal cervical length screening in singleton gestations without
264 a previous preterm birth: ten reasons why it should be implemented. *Am J Obstet Gynecol*,
265 2015 Dec 19. Doi: 10.1016/j.ajog.2015.12.017

266 Miller ES, Grobman WA, Fonseca L, Robinson BK. Indomethacin and antibiotics in
267 examination-indicated cerclage: a randomized controlled trial. *Obstet Gynecol*, 2014;
268 123:1311-6

269 Roman et al. Cerclage in twin pregnancy with dilated cervix between 16 to 24 weeks of
270 gestation: retrospective cohort study. *Am J Obstet Gynecol*. 2016 Jul;215(1):98.e1-98.e11.
271 doi: 10.1016/j.ajog.2016.01.172. Epub 2016 Jan 28.

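### The monthly digital examination is done only in the pessary arm, at visits where adverse events are recorded, so the maternal side-effect comparison can be biased against the pessary

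*Protocol*

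**What the plan says.** All of the relevant care is set out in one paragraph of the protocol section on intervention and control group management.

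- Control care: "Women in the control group will receive the same obstetrical care as those in the study group".
- Visits, both arms: "All the participants will be followed in outpatient settings every month until delivery".
- Pessary arm only: "a digital exam will be done at each of these monthly visits to assure proper" placement. No digital examination is scheduled for controls.
- Recording, not restricted to one arm: "At any follow-up visit, TVU CL and assessment of adverse events will be" recorded.

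Earlier in the same section, the baseline examination is common to both arms: "At the time of randomization, all women will undergo a speculum examination".

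The section on primary and secondary outcomes lists "Maternal side effects" without a definition, an event list or a way of eliciting them. The same list does define chorioamnionitis, neonatal death, perinatal death and the perinatal composite.

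**The concern.** A harm comparison is fair when an event has the same chance of being noticed in either arm. Here one arm has an extra hands-on vaginal examination at the very visits where adverse events are written down. Discharge or slight bleeding that the woman has not mentioned can be noticed at that examination and recorded. The same finding in a control could go unnoticed.

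Maternal side effects are the only named maternal tolerability outcome for the device. If the pessary arm shows an excess, part of it may come from the extra examination, and the data could not separate that part from an effect of the device. An analysis plan cannot repair this later, because the separation needs a record, made at the visit, of how each event came to light. The protocol itself creates the imbalance by scheduling the examination in one arm.

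**Working it through.** **Plan's own figure.** The only sample-size figure is 300 women (150 per group) for SPTB before 34 weeks. For 25% against 12.5%, two-sided 5% and an assumed 80% power (the protocol states none), the uncorrected two-proportion formula gives 152 per arm, 304 in all, in line with 300. This point does not touch that figure. The plan gives no figure for side effects.

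**Number of placement checks.** Randomisation is at 18 0/7 to 23 6/7 weeks (Summary) and removal is from 37 0/7 (management section).

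- Longest: 37 − 18 = 19.0 weeks; 19.0 / 4.345 weeks per month = 4.4.
- Shortest: 37 − 23.86 = 13.1 weeks; 13.1 / 4.345 = 3.0.

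So k is about 3 to 4 checks per pessary woman and none per control. Early birth or early removal lowers k.

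**Illustration (assumed rates).** Let b be the share of women who report symptoms, equal in both arms. Let q be the chance per check of an event found only there in a woman who would otherwise have none recorded. Events provoked by the check are not in q.

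- Found at least once: e = 1 − (1 − q)^k
- Recorded in the pessary arm: p1 = b + (1 − b)e; in controls: b
- Share of pessary-arm women counted only through the check: (p1 − b)/p1
- Odds ratio: [p1/(1 − p1)] / [b/(1 − b)]
- Rejection by a two-sided 5% z test, 150 per arm: Φ((d − 1.96 s0)/s1) + Φ((−d − 1.96 s0)/s1), with d = p1 − b, s0 = √(2p̄(1 − p̄)/150), s1 = √((p1(1 − p1) + b(1 − b))/150) and p̄ = (p1 + b)/2

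Example with b = 0.20, q = 0.01, k = 4: e = 1 − 0.99^4 = 0.0394; p1 = 0.20 + 0.80 × 0.0394 = 0.2315; share = 0.0315/0.2315 = 13.6%; odds ratio = (0.2315/0.7685)/0.25 = 1.21; rejection 10.2%.

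| b | q | Share, k = 3 to 4 | Odds ratio | Rejection with no true difference |
|---|---|---|---|---|
| 10% | 0.5% | 11.8% to 15.2% | 1.15 to 1.20 | 6.6% to 7.9% |
| 20% | 0.5% | 5.6% to 7.4% | 1.08 to 1.10 | 5.8% to 6.3% |
| 20% | 1% | 10.6% to 13.6% | 1.15 to 1.21 | 7.9% to 10.2% |
| 20% | 2% | 19.0% to 23.7% | 1.31 to 1.42 | 16.4% to 24.7% |
| 40% | 0.5% | 2.2% to 2.9% | 1.04 to 1.05 | 5.3% to 5.5% |
| 40% | 2% | 8.1% to 10.4% | 1.16 to 1.21 | 9.5% to 12.9% |

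**Second illustration.** Take equal true rates of 10% to 40% and let the chance of detecting an event differ by arm. Detection of 0.85 against 0.80 gives a risk ratio of 0.85/0.80 = 1.06 and rejection of 5.3% to 6.6%. Detection of 0.90 against 0.80 gives 1.13 and 6.1% to 11.3%. Detection of 0.90 against 0.60 gives 1.50 and 17% to 62%.

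Both illustrations run from negligible to material, and the protocol gives nothing to place the trial within either. The first treats checks as independent of each other and of reported symptoms, and gives every pessary woman the full 3 to 4. Overlap with reported symptoms, or fewer checks, lowers the result. The rule "The treatment effect will be tested at the two-tailed 5% level" stands under the primary analysis. The protocol names no test for side effects, so the rejection rates show scale only.

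**The case against.** The best objection is that the examination exists only because there is a pessary to check. In an intention-to-treat comparison of assignment to pessary or no pessary, spotting or discomfort caused by the check is a true harm of being assigned the device. This stands. A reader might infer that every event linked to the examination is spurious and should be removed from the pessary arm. The documents do not support that. Such a removal, applied to one arm on the judgement of open-label staff, could undercount real harm and favour the device. Only events found by the check, which would otherwise have gone unrecorded, are a detection problem.

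A second objection is that most ascertainment is already equal: monthly visits, adverse-event assessment and a transvaginal scan are the same in both arms, and the scan is itself a vaginal examination of at least five minutes. The digital examination is described as a placement check, not a search for side effects. This also stands, and it limits the likely size. A reader might infer that controls are followed less closely in general, or that the harm comparison is shown to be biased; the text supports neither. But the purpose of an examination does not decide what is noticed at it, and nothing keeps what is noticed out of that visit's adverse-event record.

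Third, symptom lists and CRF fields are often left to other documents. That is fair for the detail. The unequal examination is fixed in the protocol, and that is the point here. The sentence on equal care is qualified in the same paragraph, so it needs only a clarification.

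**Conclusion.** The point holds as a possible bias in one secondary outcome. The protocol schedules an extra vaginal examination in the pessary arm, at the visits where adverse events are recorded, and compares side effects without a common way of eliciting them. Any events found only at that examination raise the pessary-arm count.

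The size is unknown, because neither the symptom rate nor the detection rate is in the documents. Over the assumed rates tabulated, the share of pessary-arm women counted only through the check runs from about 2% to about 24%, and it is zero if the check reveals nothing that the visit would not otherwise record. Masking does not settle the matter: the imbalance would remain with a blinded recorder, because what differs is the examination. SPTB before 34 weeks and the sample size of 300 are unaffected. Severity: minor.

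**What to change.** Leave clinical care as it is and change only how side effects are elicited, recorded and reported.

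1. Base the between-arm comparison on symptoms asked in both arms with one identical fixed list (discharge, bleeding, pain or discomfort) at each monthly visit, before any vaginal examination or scan.
2. Add a CRF field for how each event was detected: reported by the woman, or first found at the placement check.
3. Keep every reported symptom in the comparison, including any that the examination may have provoked.
4. Report events found only at the placement check separately for the pessary arm, and also show the comparison with all events included.
5. Reword the sentence on control care so that it excepts the pessary and its monthly placement check.

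The cost is a short list, one CRF field and a wording change, with no extra visit or procedure. The downside is that the headline comparison leaves out findings made only at the placement check. They remain visible in the separate report and in the all-events comparison.

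### The blinding claim for outcome assessors and data collectors is untenable for side effects and cervical length recorded at visits, and unsecured for the spontaneous/indicated label behind SPTB <34 weeks

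*Protocol*

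**What the plan says.** Protocol, Randomization and masking: the study is open label because of the "nature of the intervention, but the outcome assessors, data collectors, and data analysts will" be "blinded to the allocated treatment group". No outcome or role is exempted, and no procedure for achieving the blinding is given.

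Protocol, Intervention group and control group management: all women are seen monthly until delivery. In the "pessary group, a digital exam will be done at each of these monthly visits to assure proper" placement of the device. The next sentence covers the same visits: "pessary placement. At any follow-up visit, TVU CL and assessment of adverse events will be" recorded. The progesterone rule follows at once, for CL of 20 mm or less: "recorded. For TVU CL ≤ 20 mm, women in both groups will be all recommended vaginal" progesterone. The device stays in until the 37th week unless it is removed early; bleeding, preterm labor, severe discomfort and the woman's request are among the listed reasons.

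Protocol, Measurement of cervical length: the scan uses a transvaginal probe "placed in the anterior fornix of the vaginal. Endocervical canal length will be measured as the" distance between the internal and external os.

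Protocol, Quality control and handling of data: "Data on pregnancy outcomes were obtained from hospital maternity records. In case of PTB", "records were examined to determine whether the delivery was medically indicated (indicated" PTB) or spontaneous. Spontaneous means spontaneous onset of labor or preterm rupture of membranes. The section does not say who examines the records or in what form.

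Protocol, Primary and secondary outcomes: the primary outcome is SPTB <34 weeks. Maternal side effects are a secondary outcome. CL during follow-up is not listed.

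**The concern.** A masking statement tells readers how far to trust outcomes that involve judgement. Here it covers everyone who assesses or collects data, while the visit schedule puts some of those people in direct contact with the device. If the trial is reported as having blinded assessors and data collectors, side-effect comparisons will look better protected than they are.

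More is at stake for the primary outcome. Gestational age at birth is objective, but whether an early birth counts as an event depends on calling it spontaneous or indicated. The same label feeds SPTB <37, <32 and <28 weeks, and the Kaplan-Meier analysis, where elective deliveries are censored. If the reader of the records knows the arm, borderline cases can be sorted differently by arm.

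Follow-up CL matters by another route. As the text is ordered, a reading of 20 mm or less at a visit appears to lead to a progesterone recommendation. An unblinded reading could then influence co-treatment by arm.

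**Working it through.** **Step 1: the masking claim against each kind of data**

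| Data | How obtained | Can the blinding claim hold? |
|---|---|---|
| Maternal side effects | Recorded at monthly visits, from women who know their arm; only one arm has the digital exam | No, on any ordinary reading of the visit |
| Follow-up CL | Vaginal scan at the same visits, device in place in one arm | No, for the same reason; not an outcome |
| Spontaneous/indicated label | Judged from hospital maternity records | It can, but nothing described secures it |
| Gestational age at birth | Dated by menstrual history and ultrasound | Objective; little depends on blinding |
| Statistical analysis | Data analysts | Not contradicted anywhere |

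The first two rows are strong inferences from the procedures; the protocol does not say outright that these staff learn the arm. In the third row, a woman still wearing the device who delivers before 34 weeks has it removed around that delivery. Her maternity record would ordinarily mention it. That too is an inference.

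**Step 2: the plan's own figure**

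Inputs from Sample size and Primary analysis: 25% in controls, a 50% reduction (so 12.5%), 150 per group, two-sided 5%. No power is stated; 80% is assumed here.

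n per arm = [1.96·√(2·0.1875·0.8125) + 0.8416·√(0.25·0.75 + 0.125·0.875)]² / 0.125²
= (1.0819 + 0.4586)² / 0.015625 ≈ 152, or 304 in total.

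The planned 300 is reproduced to within about 1%; power at 150 per arm is 79.5%. Expected events are 0.25 × 150 = 37.5 and 0.125 × 150 = 18.75, together about 56.

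**Step 3: sensitivity to the label (assumed rates)**

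The protocol gives no misclassification rate, so a range is needed. Take no true effect and a 25% rate in both arms. Let a fraction f of pessary-arm events be labelled indicated, so that the observed pessary rate is 0.25(1 − f). The test is z = (p_c − p_p)/√[p̄(1 − p̄)·2/150], rejecting when |z| > 1.96, over 400,000 simulated trials per row. It is unadjusted, whereas the planned analysis is logistic regression with CL as a covariate.

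| f | Events moved (of 37.5) | Apparent OR | Two-sided false-positive rate |
|---|---|---|---|
| 0 | 0 | 1.00 | 5.0% |
| 5% | 1.9 | 0.93 | 5.7% |
| 10% | 3.8 | 0.87 | 8.0% |
| 20% | 7.5 | 0.75 | 18.0% |
| 30% | 11.3 | 0.64 | 35.6% |

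OR example for f = 10%: (0.225/0.775) / (0.25/0.75) = 0.87.

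A handful of births sorted differently by arm is thus enough to matter. The table does not show that this will happen, or in which direction.

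**The case against.** The best defence is that the sections can be reconciled. Data collectors may mean the people who extract pregnancy outcomes, not the clinic staff. Blinded record review is feasible, and the protocol promises it; how it is done may be set out in a document not shown. SPTB has a definition, so the label is not free judgement. CL used for eligibility and stratification is measured before allocation, by certified operators to a fixed technique, and the progesterone threshold is the same number in both arms. Any imbalance in progesterone could reflect a real effect of the pessary on CL, or simply open-label care.

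Much of this stands, and it rules out stronger readings. A reader might infer that masking of the primary outcome does not exist. The documents do not support that: they do not say that the records show the arm, or who reads them. A reader might count CL as an outcome assessed unblinded; it is not an outcome. A reader might also want one figure for the bias, such as two births moved in each arm, shifting the difference by (2 + 2)/150 = 2.7 points. Nothing in the protocol supports those counts, and moving control births to spontaneous needs an indicated-birth rate that is not given.

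What does not stand is the defence of the blanket sentence. It exempts no one, and side effects are a listed outcome collected at visits that reveal the arm. Nor is the label merely a detail left for later: the protocol itself names the source, and that source would ordinarily undo the promise unless someone prepares it.

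**Conclusion.** The point holds in two parts of different strength. For maternal side effects and follow-up CL, the blinding statement conflicts with the protocol's own visit procedures and should not be made. For the spontaneous/indicated label, blinding is asserted without any step that would secure it. The second part rests on the assumption that maternity records mention the pessary.

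The size is conditional. If 5% to 20% of pessary-arm events were relabelled under no true effect at 25%, the false-positive rate would be about 6% to 18%. Those fractions are assumptions; relabelling in the other direction would hide a benefit. The progesterone route is less certain still: it depends on the threshold applying to follow-up readings, as its placement suggests. Analyst blinding is not in question. The change should be made, but the documents do not show that the primary comparison is biased.

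**What to change.** 1. In Randomization and masking, restrict the blinding statement to the outcomes and roles for which it can hold, and state that adverse events and CL at visits are recorded unblinded.
2. In Quality control and handling of data, have the planned blinded assessor classify births before 37 weeks as spontaneous or indicated from a delivery extract. Staff who already know the arm first remove pessary and allocation text, and they take no part in the classification.
3. Keep the analysts on coded arms.
4. Tabulate progesterone starts by arm and CL stratum (≤20 mm, >20–25 mm). This is description only and changes no clinical rule. The >20–25 mm stratum is where a later reading could lead to a start.

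The cost is some wording, a less favourable masking statement, and clerical redaction for the preterm births only. On the planned rates that is about 56 SPTB <34 records, plus the other births before 37 weeks, whose number the protocol does not give. No further assessor is needed, but the person who redacts must not be the one who classifies.
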